The interventions included in the SBIRT system are the Common Elements Treatment Approach-Brief Intervention (CETA-BI) and the full CETA psychotherapy (CETA). Previous randomized controlled trials have found CETA to be an effective treatment, including among refugees, for a range of mental and behavioral health problems, including depression, anxiety, trauma, and functional impairment. 15-17 CETA has recently been tested in Zambia and found to also reduce unhealthy alcohol use in addition to mental health problems and intimate partner violence. 17 CETA is a transdiagnostic approach, meaning that counselors trained in CETA are equipped with the ability to treat a range of co-occurring mental and behavioral health conditions. It was developed for use in low- and middle-income countries (LMIC) to facilitate lower cost and sustainability. CETA includes 9 cognitive behavioral elements found in most evidence-based psychological treatments. 18 CETA is 6-12 weekly one-hour sessions with flexibility depending on symptom severity. CETA-BI combines motivational interviewing skills with cognitive behavioral therapy to assist clients in considering changing their rates of AOD use. The intervention lasts 30-40 minutes and consists of 6 components including: 1) screening; 2) identifying the impacts of unhealthy AOD use; 3) talking about change and goal-setting; 4) understanding the primary reason for drinking; 5) skill building; and 6) referral for services. CETA-BI and CETA were previously found effective for AOD use and mental health problems within HIV care in Lusaka, Zambia. 19 CETA-BI and CETA have significant potential for adaptation and implementation in refugee settings but a rigorous RCT adapting and testing them in an SBIRT stepped-care approach among refugees is warranted.

All SBIRT components will be delivered by lay counselors. Counselors will already have been trained in the SBIRT interventions through our formative work in Mantapala (IRB AAAT1592). This enhances feasibility, scalability, and sustainability. Further, all aspects of the SBIRT are designed to be flexible: the

screening, the provision of the BI, and the referral for treatment and provision of full CETA can be done in the community and in locations where clients feel comfortable.

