## **E. PROCEDURES**

## E.1 Procedures for RCT

### E.1a Recruitment

The trial will feature several recruitment strategies. First, community meetings will take place at each of the 20 settlement blocks/administrative units and in the surrounding host community. At these meetings we will describe the study in detail and also answer questions and any concerns that community members have. We will provide information on times and places in the community where interested individuals can meet privately with research staff to learn more about the study. Second, we will ask providers within the settlement health clinics and protection programs as well as community leaders to introduce the study to individuals who they believe may have unhealthy alcohol or other drug use. We will provide them with a recruitment script for this purpose. Interested individuals will be given the contact information of the research team to schedule a time to receive more information and also will be able to provide their own contact information if they want so that the research team can contact the individual.

These recruitment strategies ensure that only potential participants who have expressed interest in hearing more about the study (at the community meetings, to a community leader, or to a provider at a health clinic or protection program) will be in contact with the study team.

Recruitment activities will be conducted by the Zambia-based team at WiLDAF and CARE Zambia. Columbia investigators will not be involved in the recruitment process and will not interact directly with potential study participants.

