### E.1e Randomization and Enrollment into the Trial

Participants who complete the full baseline assessment and are fully eligible for the trial (have met all inclusion and no exclusion criteria) will be randomized and enrolled into the RCT. Randomization will be on a 1:1 basis, stratified by gender and site (Mantapala settlement or host community) and symptom severity (low or moderate/high). Participants will be randomized to SBIRT or treatment as usual (TAU) control. The RA will allocate participants to study conditions using a series of sealed, opaque envelopes. RAs and data analysts will be blinded. Participants will be notified immediately about the result of the randomization.

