# E.1f Interventions

- SBIRT. All participants randomized to SBIRT will receive an on-the-spot alcohol brief intervention (CETA-BI) and be categorized as low or moderate/high severity. Moderate/high severity is defined as one or more of: (a) AUDIT scores indicating moderate-to-severe AUD (≥12 for women; ≥16 among men); (b) meeting validated symptom criteria for depression (≥16 on CES-D),  (c) trauma/anxiety (≥2.5 on HTQ),  (d) substance use (≥27 on ASSIST).  Participants who are low severity will not receive any additional treatment. Participants who are moderate/high severity will be connected to a CETA counselor and will begin full CETA treatment. This will involve approximately 6-12 weekly CETA sessions. CETA sessions will be conducted in a private setting mutually agreed upon by the counselor and participant (this could be in the health clinic or some other community-based setting where the participant feels comfortable). Data collected for these intervention participants will include the Improving Your Health worksheet (during the BI session), the Client Monitoring Form (during CETA sessions) and the Alcohol Timeline Followback (completed at both the BI and subsequent CETA sessions. All of these measures are included in Rascal.
- TAU. In October 2019, Mantapala health workers and supervisors were trained in mhGAP-HIG, which is a mental health service provision guide for use in humanitarian settings; this training was led by staff from United Nations High Commissioner for Refugees. This training did *not* include evidence-based psychological interventions (e.g., CETA). Participants randomized to TAU will be referred to the existing services that exist in the health clinic located in Mantapala refugee settlement. This clinic is staffed by eight clinical staff who provide clinical assessments, primary care, basic counseling, and limited specialized services (e.g., maternal and child care, HIV treatment). More specialized services are referred to the District Hospital in Nchelenge, which is the nearest town approximately 50 kilometers away.

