## E.2 Procedures for Implementation Interviews

### E.2a Recruitment

We will conduct implementation interviews with a subset of participants enrolled in the RCT as well as other relevant stakeholders. Participants in the implementation interviews include participants enrolled in the RCT who received SBIRT (n=30), SBIRT counselors (n=15), or is a humanitarian policymakers or program officials whose position has relevance for the implementation of SBIRT in humanitarian settings (n=15). We will purposively recruit a subset of 30 RCT participants who received SBIRT selected using maximum variation sampling to ensure they represent both refugee and host community members, participants with a range of alcohol and substance use patterns at baseline, and variations in attendance and intervention response. Participants will be invited to complete the implementation interview by the RA at their 6-month follow-up interview. Fifteen SBIRT counselors will be invited by an RA to participate in an implementation interview at the end of their final SBIRT session. We will purposively select counselors to reflect variation in the following characteristics: number of SBIRT and CETA sessions delivered, community membership (refugee vs. host), and competency as identified by the clinical supervisor. Fifteen humanitarian stakeholders (e.g., policymakers and program officials) will be invited to participate in the study interview by a member of our research team throughout the study period. We will select these stakeholders based on their knowledge of the project and the relevance of their role in its implementation.

Recruitment activities will be conducted by the Zambia-based team at WiLDAF and CARE Zambia. Columbia investigators will not be involved in the recruitment process and will not interact directly with potential study participants.

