### F. STATISTICAL PROCEDURES

Provide sufficient details so that the adequacy of the statistical procedures can be evaluated including power calculations to justify the number of participants to be enrolled into the study. Definitions of subject terms such as enrolled and accrued as used for Rascal submissions can be found in the Subjects section

The primary outcome is the difference in change in AUDIT score from baseline to 12-month follow-up between SBIRT and TAU. Using baseline data from an ongoing study of CETA-BI + Full CETA in Lusaka, we estimated the sample size required to estimate a moderate treatment effect (Cohen's d=0.5) with 90% power would be 172 (86 per arm). Given the stratified sampling, clustering, planned subgroup analyses, and possible attrition, our study will require a total sample size of 400.

The primary analysis will use mixed effects regression to estimate the difference in change in AUDIT scores between the treatment groups. Secondary analyses will include: a) treatment effectiveness for secondary outcomes; b) moderator/subgroup; c) mediators; d) predictors of treatment completion; e) longitudinal analysis of weekly symptom change (on the CMF and Alcohol TLFB for CETA participants; and g) mixed methods analysis based on best practice guidelines for exploring implementation data.

Qualitative data from the implementation interviews will be transcribed and any identifiable information will be redacted. Once transcribed, the audio recordings will be destroyed. These data will then be analyzed by members of the research team using thematic analysis whereby research staff read the full set of transcripts and develop codes using a subset of those transcripts. Once a codebook has been developed, it will be applied to the full set of transcripts with codes added as needed. We anticipate the main domains will include adoption, acceptability, appropriateness, feasibility, and reach/access of SBIRT.

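### Does the primary AUDIT model need a prespecified counselor effect because the plan cites clustering without defining it?

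*Combined protocol and SAP*

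**What the plan says.** Section F defines the endpoint: "The primary outcome is the difference in change in AUDIT score from baseline to 12-month follow-up between SBIRT and TAU". It derives 172 participants (86 per arm) for Cohen's d of 0.5 at 90% power, then moves to 400: "Given the stratified sampling, clustering, planned subgroup analyses, and possible attrition, our study will require a total sample size of 400". This is the only mention of clustering in the document. The model gets one sentence: "The primary analysis will use mixed effects regression to estimate the difference in change in AUDIT scores between the treatment groups". No random effects are listed.

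The design has to be pieced together from other sections. Section E.1e randomizes individuals: "Randomization will be on a 1:1 basis, stratified by gender and site", and also by symptom severity. Section B states: "All SBIRT components will be delivered by lay counselors". Section E.1f describes the comparator: "Participants randomized to TAU will be referred to the existing services that exist in the health clinic located in Mantapala refugee settlement". The total number of counselors is not given. The nearest figure is in the implementation study, section E.2a: "Fifteen SBIRT counselors will be invited by an RA to participate in an implementation interview". Those fifteen are chosen purposively, so the total may be larger.

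**The concern.** The design looks partially nested. SBIRT participants are grouped under counselors, while TAU participants have no counselor from the study. A participant-level random effect deals with repeated AUDIT scores from one person. It does not deal with correlation among clients of the same counselor. If counselors differ in their effect and are left out of the model, the variance of the SBIRT mean is understated and the primary interval is too narrow.

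The plan gives some reason to expect differences, since section E.2a samples counselors for variation in competency and in sessions delivered. A larger sample would not cure the problem: it restores power but does not correct a standard error taken from the wrong model. Leaving the random effects unstated also allows the choice to be made after the data are seen.

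**Working it through.** **1. The plan's own figure.** Inputs from section F: d = 0.5 and 90% power. Alpha is not stated; 0.05 two-sided is assumed. The normal approximation gives n = 2(1.960 + 1.282)² / 0.5² = 84.1, so 85 per arm. The noncentral t calculation gives 86 per arm (power 0.903), which is 172 in total. The base figure reproduces. The step to 400 is a factor of 400/172 = 2.33 and cannot be reproduced, because no ICC, cluster size or attrition rate is given.

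**2. Size of the effect if counselor is omitted.** Assumptions, none from the documents: 20% attrition (160 analysed per arm), K = 25 or 15 counselors with equal caseloads, ICC of 0.02, 0.05 or 0.10, and the same ICC for every SBIRT participant. The formulas are:

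- caseload m = 160/K
- design effect in SBIRT, DE = 1 + (m − 1) × ICC
- true over naive variance of the arm difference, r = (DE + 1)/2
- type I error = 2 × [1 − Φ(1.96/√r)]

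| K | m | ICC | DE | r | Type I error |
|---|---|---|---|---|---|
| 25 | 6.4 | 0.02 | 1.108 | 1.054 | 5.6% |
| 25 | 6.4 | 0.05 | 1.270 | 1.135 | 6.6% |
| 25 | 6.4 | 0.10 | 1.540 | 1.270 | 8.2% |
| 15 | 10.7 | 0.02 | 1.193 | 1.097 | 6.1% |
| 15 | 10.7 | 0.05 | 1.483 | 1.242 | 7.9% |
| 15 | 10.7 | 0.10 | 1.967 | 1.483 | 10.8% |

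Simulation with 15 counselors (40,000 trials per setting) gives 6.0%, 7.8% and 10.7% at the three ICCs, and 5.0% at ICC 0. With no attrition (200 per arm) the formula gives 5.8% to 12.3% over the same grid.

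**3. Sensitivity to the uniform ICC.** Under section E.1f, low-severity participants receive only the brief intervention, and the rest go on to a CETA counselor. Suppose counselor effects arise only in full CETA, and let p be the low-severity share (not given). Then m = 160(1 − p)/K and DE = 1 + (1 − p)(m − 1) × ICC. With p = 0.5, K = 15 and ICC 0.10: m = 5.33, DE = 1.217, r = 1.108, type I error 6.3%. Over the whole grid the range is 5.1% to 6.3% for p = 0.5 and 5.3% to 8.1% for p = 0.25.

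**4. Is 400 too few?** In the worst row above, 160 per arm is worth 160/1.483 = 108 independent participants per arm, against the 86 required. With counselors modelled and Satterthwaite degrees of freedom, power at d = 0.5 is 94.5% to 99.0% across the grid.

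**5. Groupings that cross the arms.** Section E.1a says "community meetings will take place at each of the 20 settlement blocks/administrative units and in the surrounding host community". Blocks and sites contain participants from both arms, so ignoring them does not inflate the arm contrast. With 15 or 20 such areas and 200 per arm, a naive test rejects 4.8% to 5.1% at ICC 0.05 to 0.10.

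**6. What an SBIRT-only counselor effect would do.** The documents do not say how participants are assigned to counselors. Suppose assignment follows area: 16 areas, one counselor each, 10 participants per arm per area, and no true counselor effect. The SBIRT-only model attributes area variation to counselors, although that variation is shared with TAU. In simulation it then rejects about 3.5%, 2.6% and 1.5% at area ICC 0.02, 0.05 and 0.10, against a nominal 5%.

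**The case for a change.** The strongest opposing case is that the omission is real and cheap to close. Section F's own template asks for enough detail to judge the statistical methods. A few lines and a counselor identifier would settle the matter, and an identifier not kept now may be hard to recover. It stands that the document names neither the clusters nor the random effects. The arithmetic under the stated assumptions stands as well.

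The rest is weaker. That counselors treat only SBIRT participants is a sound inference from sections B and E.1f, but the documents do not state it. The error-rate figures describe an average effect of exactly zero with counselors still differing, so that some help and others harm. If SBIRT affects no one there is no inflation. Otherwise the issue is how far the interval should generalize to other counselors, and whether to treat counselors as fixed or random for that purpose is open to debate.

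Nor is the remedy free. It can overcorrect, as step 6 shows. It treats TAU clients as independent although they may share the eight clinic staff in section E.1f. A counselor identifier that exists only for SBIRT participants also shows the arm to data analysts, whom section E.1e says are blinded. That blinding itself gives some protection against a choice of model driven by the result.

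**Conclusion.** No change follows. Section F recognizes clustering and chooses a class of model that can handle it. Nothing in the text excludes a counselor term, and no stated rule is shown to give a wrong answer. An analyst fitting this model has to choose its random effects, and counselor is an obvious candidate to consider.

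Harm would need both an omitted counselor term and real differences between counselors, and the documents establish neither. If both held, the two-sided error rate could lie between 5.6% and 10.8% with 160 per arm, 15 to 25 counselors and ICC 0.02 to 0.10. It would be 5.1% to 6.3% if half the arm received only the brief intervention and counselor effects were confined to full CETA. The arm difference itself is not biased by this mechanism, and 400 leaves at least 94.5% power over the assumed grid with counselors modelled. Whether to adopt an SBIRT-only counselor effect is a fair trade-off that depends on how counselors are assigned, which the documents leave open.

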## G DATA CUSTODY, SECURITY, AND CONFIDENTIALITY PROTECTIONS

All data will be collected in Zambia by WiLDAF and CARE Zambia staff. Columbia investigators will not be involved in any data collection activities and will not have access to any sensitive data or identifying information from participants.

Confidentiality of study data is a priority, and we will take many precautions to protect against the possibility of a breach of confidentiality. All research staff are aware of the importance of maintaining strict confidentiality and we have extensive experience dealing with sensitive mental health/alcohol,

substance use data in Zambia. The following precautions will protect the privacy of participants and maintain confidentiality of research data:

- 1) All study staff will be well trained and will receive ongoing supervision in confidentiality and data security procedures, specifically in ethical conduct, confidentiality protection, mandated reporting, and other topics of human participant protection.
- 2) Privacy will be maintained by conducting all data collection activities in private areas at WiLDAF and CARE Zambia sites in Mantapala or in private locations preferred by study participants (community locations with private spaces, for example, if this is preferred for CETA sessions). Data (both electronic and paper) will be transported daily in secure private study vehicles from Mantapala to the study team's office building in the town of Kawambwa headquarters building where they will be stored in locked rooms in locked filing cabinets and computers.
- 3) Each participant will be assigned a unique study ID number, and all data (e.g., ACASI data, CMF/TLFB data, implementation data) will be coded with ID numbers only and will not contain identifying information. These data will be stored on the encrypted system with restricted access to essential investigators and staff. We will not obtain signatures on the consent form/information sheet. We will only collect sensitive data/identifying information (names, phone numbers, and addresses) from participants for purposes of contacting participants to schedule study visits. An encrypted spreadsheet linking participant names, phone numbers, and addresses with ID numbers will be stored separately from the coded data. This personally identifiable information will be stored on an encrypted endpoint computer in a locked office within the study office in Kawambwa. Only essential staff for conducting participant follow-ups will have access to this file. Columbia personnel will not have access to sensitive data/identifying information. Following the end of the study, the link and all personally identifiable information will be destroyed such that all data are completely de-identified.
- 4) Paper-based data (Client Monitoring Form, Alcohol TLFB, and Improving Your Health worksheets, and notes taken during qualitative interviews and discussions) will be coded and securely stored in locked file cabinets in the study team's locked offices. They will be entered into an encrypted database stored on an encrypted shared data system.
- 5) Qualitative interviews in Aim 2 will be recorded with permission from the participants (no other activities will have audio recording). Recordings will be destroyed after interviews are transcribed. We expect transcription of audio files to be done within one to two weeks after the interview session. The oral study introduction will not be included in the recording and we will train research assistants to avoid mentioning personal identifying information during the course of the interview. Any personal information that is discussed during the interview will be redacted from study transcripts.
- 6) ACASI data will be stored temporarily locally on password-protected laptop computers and once transported to the study office (daily) will be removed from the laptops and uploaded to the encrypted system. No identifying information will be included in the coded ACASI data (only an ID number). Access to data storage areas and computers will be restricted to essential study staff.
- 7) Only coded data will be shared with U.S.-based study investigators at Columbia University via an encrypted shared system. Only IRB-approved Columbia investigators will have access to the coded data. Columbia investigators will not have access to personally identifiable information/sensitive data. In

Zambia, access to personally identifiable information/sensitive data will be restricted to essential personnel.

- 8) Analysis will occur only on coded (for analysis while study is ongoing) or deidentified (following completion of the study) data and be presented in aggregate.
- 9) All participants will be encouraged to contact the local study director, local investigators, or other staff to report any undesirable conduct associated with the study. These reports will be brought to the attention of the study director, local PIs and co-Is and the MPIs, and appropriate steps will be taken to solve the problems, including reporting to relevant ethical review boards.

#### H. POTENTIAL RISKS

H.1 Privacy/Breach of Confidentiality. A breach of confidentiality is a risk of the study, but we believe is unlikely due to precautions described in section G.

H.2 Emotional Distress. Data collection may be associated with minimal emotional discomfort due to the discussion of sensitive topics such as substance-related problems, however, we do not believe that this will be frequent or severe. We will train research assistants to identify acute distress among participants, respond in a supportive manner, and provide them with referral resources. The study is being conducted in collaboration with [name], a clinical psychologist and developer of CETA, as well as [name], a clinical social worker and expert CETA trainer. [name] and [name] will be available to oversee all situations in which additional expertise is needed. If participants require additional mental health or protection services, we will assist them in accessing the Mantapala or nearby Nchelenge health facility.

Pilot participants may experience emotional distress as a result of participation in the interventions. Many therapeutic interventions deal with small degrees of stress within a session as part of the treatment. Based on research and experience, the expected degree of distress will be minimal and expected as part of the therapeutic process. In cases where distress does occur during treatment, the participant would be with a trained CETA counselor who will be trained at handling such situations. In addition, these counselors will have local clinical supervisors and access to [name] and [name], as well as to [name], study investigator and psychiatrist on the research team based at University of Zambia. Our team has run multiple trials with CETA, including in Zambia, and have established safety protocols for evaluating and referring patients for urgent care when necessary. We are prepared to handle more significant issues that could arise and have established relationships at referral psychiatric hospitals, such as Chainama Hills Hospital in Lusaka, which has inpatient psychiatric services. Should it be necessary, participants can be referred and receive treatment there. [name] will also be available for virtual consultations as needed.

H.3 Alcohol/Substance Withdrawal. Study counselors are highly trained by [name] and [name] to identify signs and symptoms of withdrawal. They will be trained to immediately contact their clinical supervisors who will evaluate the participants and provide immediate referral for appropriate care, including facilitating transport to in-patient services in Nchelenge and consultations with [name] and his team.

